**Pilot randomized trial to assess the effects of an antimicrobial mouthwash on the esophageal and gastric microbiome**

**NCT02513784**

**Protocol version: 03.11.2021**

The incidence of esophageal adenocarcinoma (EAC) has risen nearly 10-fold over the past half century, yet the reasons for this dramatic change are largely unknown. During this same time period, the gastrointestinal microbiome has undergone a significant shift with the advent of antibiotics and the progressive decline in *Helicobacter pylori* infection rates. This raises the possibility that the upper gastrointestinal microbiome may play a key role in the development of BE and EAC. The esophageal microbiome in patients with reflux esophagitis or Barrett's esophagus (BE, the precursor to EAC) is heavily populated with Gram-negative bacteria, which may drive a chronic inflammatory, pro-neoplastic state. Also observed is an increased abundance of *Fusobacterium nucleatum*; work by our team has shown that *F. nucleatum* may directly contribute to colon carcinogenesis, and we suspect that this species may have similar effects in promoting esophageal neoplasia. We have shown that there is a relatively high abundance of *F. nucleatum* in the gastric cardia, and in animal models chronic inflammation in the gastric cardia leads to the development of Barrett's esophagus and EAC. Thus, we speculate that the upper gastrointestinal microbiome plays a key role in the development of BE and EAC.

The esophageal microbiome is very similar to the oral microbiome; both contain an abundance of anaerobes as well as a high ratio of Firmicutes to Bacteroidetes. The microbiome of the upper gastrointestinal tract is presumably heavily influenced by migration of bacteria from the mouth via swallowed secretions. Therefore, it stands to reason that altering the oral microbiome can directly impact the microbiome of the esophagus and gastric cardia. Chlorhexidine has broad antimicrobial effects, and chlorhexidine-based mouthwashes have been used clinically for many years in the treatment of gingival and other oral diseases. Chlorhexidine mouthwash effectively reduces anaerobes and *F. nucleatum* in particular in the mouth. It also has anti-inflammatory effects (likely due to reductions in pro-inflammatory bacteria), and protects against mucositis in chemotherapy patients. We therefore propose to perform a randomized open-label pilot study to assess the effects of chlorhexidine mouthwash on the microbiome of the gastric cardia. The results of this study provide valuable information as to whether altering the oral microbiome can serve as a novel chemopreventive intervention to reduce the risk of esophageal adenocarcinoma.

This is a randomized, open-label pilot study to assess whether treatment with chlorhexidine mouthwash can alter the esophageal and gastric cardia microbiome.

We will enroll a total of 20 subjects. Patients scheduled for upper endoscopy for clinical indications will be randomized to 2 weeks of either no treatment or use of twice daily chlorhexidine mouthwash leading up to the endoscopy.

The hypotheses to be tested are:

1. Treatment with chlorhexidine mouthwash will significantly reduce the absolute abundance of *F. nucleatum* in saliva.
2. Subjects treated with chlorhexidine mouthwash will have significantly lower absolute abundance of *F. nucleatum* in the gastric cardia, compared to subjects who receive no treatment.

We will enroll patients scheduled for upper endoscopy by their treating physician and who meet the inclusion and exclusion criteria. There will be 2-3 study visits, at Day 0 and Day 14, and for

those subjects in the mouthwash arm, a final visit 1-2 weeks following the Day 14 visit. Subjects will be required to fast overnight prior to the visits on Days 0 and 14.

**Day 0:**

- Collect baseline demographic information, clinical history, medication use, and smoking history. Record height, weight, and waist and hip circumference.
- Administer a Reflux Assessment Questionnaire and a Food Frequency Questionnaire
- Saliva collection and oral swab
- Take baseline photographs of teeth (mouthwash arm only)
- Distribution of chlorhexidine mouthwash (mouthwash arm only)

**Day 14:**

- Medication reassessment
- Food Frequency Questionnaire
- Adverse event assessment
- Take photographs of teeth
- Saliva collection and oral swab (prior to endoscopy)
- Upper endoscopy (with esophageal and gastric cardia brushings and biopsies for study purposes) Optional dental cleaning visit (mouthwash arm only; 1-2 weeks after the Day 21 visit):
- Dental examination and cleaning
- Provide recommendations for follow-up dental care

**Treatment arm assignment:**

Subjects will be randomized to either twice daily chlorhexidine mouthwash or no treatment for 14 days. We will perform blocked randomization stratified by the presence of gastro-esophageal reflux (as determined by the Reflux Assessment Questionnaire) as well as by regular PPI use.

**Chlorhexidine mouthwash:**

Subjects assigned to the mouthwash arm will use a 0.12% chlorhexidine gluconate mouthwash (Peridex™; 3M ESPE Dental Products, St. Paul, MN). Subjects will be instructed to rinse 15 mL twice daily for 30 seconds and then spit. The mouthwash rinse will be performed in the morning and evening after brushing their teeth.

Subjects from both arms will be instructed to continue regular oral health care (brushing and flossing) per usual practice, although use of other mouthwashes or rinses will be prohibited during the study period.

**Concomitant medications:**

Use of other mouthwashes or rinses will be prohibited during the study period.

Any subject who takes antibiotics or immunosuppressive medications (including steroid inhalers or nasal sprays) during the study period will be excluded from final analyses.

**Photographs of Teeth:**

A potential side effect of chlorhexidine mouthwash is tooth staining. For subjects assigned to the mouthwash arm, we will take digital photographs of the teeth at Visits Day 0 and Day 14. The photographs will be used to help assess whether there has been tooth staining.

Subjects in the mouthwash arm will be offered an optional dental cleaning (below) regardless of any evidence of tooth staining as assessed by the photographs. No identifiable facial features will be visible on the images.

### **Dental examination and cleaning:**

Staining of teeth and dental hardware is a known side effect of chlorhexidine mouthwash. The expected incidence of staining after 14 days of use is difficult to predict, although it is possible that some of the subjects in the study will have staining.

For the subjects in the mouthwash arm, we will take digital photographs of the mouth at Day 0 and then again at Day 14 to assess staining.

These subjects will be offered an optional, free dental cleaning, 1-2 weeks after the Day 14 visit. During this visit we will perform a dental exam and cleaning. Based on the results of the exam, we will provide recommendations for any additional dental care that may be indicated.

### **Specimen collections:**

At the Day 0 visit we will collect saliva and also swab the inside of the mouth (cheek, tongue, hard palate, and gingiva).

This will be repeated at the Day 14 visit prior to the upper endoscopy.

During the endoscopy, the following samples will be taken for study purposes: 2 brushings (1 from normal appearing esophagus (3 cm above the gastroesophageal junction) and 1 from the gastric cardia); and 2 biopsies (one each from the esophagus and gastric cardia).

### **Microbiome and tissue analyses:**

*F. nucleatum*. We will quantitatively assess absolute abundance of *F. nucleatum* from specimens via qPCR of the FadA adhesin gene.

16S rRNA gene sequencing. At the end of the study, we will perform batched DNA extraction performed using the Qiagen DNeasy Blood and Tissue Kit (Qiagen, Valencia, CA). We will perform PCR targeting the V3 and V4 hypervariable variable regions of the 16S rRNA gene with 347f/803r primers derived from the human microbiome project. We will pool and purify samples with the QIAquick PCR kit and perform library quantification using a KAPA Library Quantification Kit (Kapa Biosystems, Wilmington, MA).

Sequencing of the 16S rRNA gene V3 and V4 regions will be performed at the New York Genome Center using the Illumina MiSeq 300PE platform (Illumina, San Diego, CA).

Based on taxonomic assignments from the 16S sequencing analyses, we will calculate relative abundance of genera and species identified in the samples. We will subsequently assign each of these taxa as Gram-negative or not Gram-negative, based on our previously assembled reference list. We will then sum the relative abundances of each of the Gram-negative taxa to calculate the relative abundance of Gram-negative bacteria for each sample.

Inflammatory Cytokines, Stem Cell Proliferation, and Intestinalization. We will perform qRT-PCR on tissue biopsies to assess for levels of NF-B, IL-1, IL-6, and IL-8. In order to assess whether Gram-negative bacteria induced inflammation may lead to BE, we will also perform qRT-PCR and IHC (with available antibodies) of markers of intestinal progenitor cell activation (Lgr5, Notch, Cck2r, Dclk1, Bmp4) and intestinalization (Cdx2, Sox2, Tff2, Tff3).

**Statistics:**

The primary outcome will be the absolute abundance of *F. nucleatum*. To address the hypothesis that chlorhexidine mouthwash reduces the absolute abundance of *F. nucleatum* in the mouth, we will assess within individual differences in subjects treated with chlorhexidine and in those who received no treatment.

We will calculate mean and standard deviation for the within-individual change in *F. nucleatum* for the treated and untreated arms. These two means will then be compared using t-tests. For the primary analysis will use data from the saliva samples, and will then perform secondary analyses with data from the oral swab samples.

We will then address the hypothesis that subjects treated with chlorhexidine have lower abundance of *F. nucleatum* in the gastric cardia compared to those who did not receive treatment. We will calculate the mean absolute abundance of *F. nucleatum* in the cardia of the treated and untreated groups, and compare means using t-tests. We will then analyze data in a similar fashion from esophageal brushings in secondary analyses. All analyses will be 2- sided. For the primary analyses, statistical significance will be defined as  $p < 0.05$ .

We will perform numerous additional secondary analyses as part of this pilot study. For each subject and sample collected we will calculate the relative abundance of Gram-negative bacteria (%GNB). We will then make the same comparisons described above, with %GNB as the outcome. For these analyses we will use Wilcoxon rank sum tests instead of t-tests.

Additional 16S sequencing analyses. For secondary analyses related to the microbiome, sequences will be grouped into operational taxonomic units (OTUs) of 97% similarity. Using these OTU definitions, we will estimate the microbial diversity of a sample by calculating distance measures based on various metrics, including the Shannon diversity index (alpha diversity), and Unifrac. This includes adjusting for the number of taxa detected for their relative abundance (proportions). We will align a representative set of OTU sequences and assign taxonomy based on the most recent Greengenes OTU database. We will phylogenetically assess phyla-level differences in relative abundance between groups, as well as exploratory analyses of the relative abundance of individual taxa, using the BenjaminiHochberg method to adjust for multiple hypothesis testing. We will normalize data with the R packages phyloseq and DESeq2. We will perform Principal Coordinate Analysis (PCA) and Hierarchical clustering of specimens based on phyla-level phylogeny or count-based distance metrics to compare groups of samples. Finally, we will perform PICRUSt analyses to estimate and compare the functional metagenomic compositions of the samples using the 16S data.

Other secondary analyses. We will compare the treated and untreated groups in terms of levels of the above prespecified inflammatory cytokines and markers of stem cell proliferation and intestinalization. We will also review the pre- and post- photographs of the mouth of the mouthwash arm subjects to determine the proportion of subjects who developed staining. The individual assessing the images will be blinded as to which images are pre- or post- treatment. We will use t-tests and Wilcoxon rank sum tests to compare continuous data and Fisher exact

tests for categorical data between groups. All analyses will be 2-sided, and statistical significance will again be defined as  $p < 0.05$ .

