**Sample Size Considerations:**

There is no published data on which to base power calculations for this study.

Prior studies have demonstrated that chlorhexidine mouthwash significantly reduces *F. nucleatum* in the mouth. However, these studies used older techniques to quantify *F. nucleatum*, and the results cannot be readily translated to expected findings using qPCR.

A sample size of 20 subjects (10 per arm) has 83% power (assuming  $\alpha = 0.05$ ) to detect a 1.3 SD difference in mean *F. nucleatum* between the groups, which likely represents a biologically meaningful difference. As this is a pilot study, we believe that in the event no significant reduction in *F. nucleatum* is observed, we will still obtain valuable data from the secondary analyses that will assist in the design of future studies aimed at altering the microbiome to reduce the risk of BE and EAC.

We anticipate that 10% of enrolled subjects will be excluded, removed, or lost to follow-up. We therefore plan to enroll 22 subjects.

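### The saliva primary analysis compares unadjusted change; a log-scale model adjusting for the Day 0 value already collected is a cheap gain in precision unless the Day 0 to Day 14 correlation is very high or Day 14 spread rises

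*Combined protocol and SAP*

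**What the plan says.** Under Statistics, the saliva analysis is built on differences within subjects: "We will calculate mean and standard deviation for the within-individual change in" *F. nucleatum* in each arm, and then "These two means will then be compared using t-tests". Saliva is the primary matrix and the oral swab is secondary. The section names no baseline covariate and no transformation of qPCR abundance.

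The Day 0 value exists for both arms. The Day 0 visit lists "Saliva collection and oral swab" with no arm restriction, while photographs and mouthwash distribution in the same list are marked as mouthwash arm only. The Day 14 visit lists "Saliva collection and oral swab (prior to endoscopy"). Specimen collections agrees: "At the Day 0 visit we will collect saliva and also swab the inside of the mouth", and "This will be repeated at the Day 14 visit prior to the upper endoscopy".

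Randomization is stratified on reflux and regular PPI use ("We will perform blocked randomization stratified by the presence of gastro-esophageal reflux"), not on baseline *F. nucleatum*. Sample Size Considerations states that "A sample size of 20 subjects (10 per arm) has 83% power" for a 1.3 SD difference, and says that no published data were available for power calculations. It does not say whether that SD belongs to the change or to a single-day value.

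**The concern.** Subtracting Day 0 is the same as adjusting for it with the coefficient fixed at 1. With equal SDs on the two days the best coefficient is rho, so subtraction over-corrects whenever rho is below 1. Two things follow. The standard error may be wider than the collected data allow. In addition, any chance Day 0 difference between arms carries over in part, with reversed sign, into the estimated effect. With 10 per arm, powered only for a large effect, either could matter to Hypothesis 1.

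**Working it through.** **The plan's own figure.** With 10 per arm and a 1.3 SD difference, 1.3/sqrt(2/10) = 2.907, and the normal probability at 2.907 - 1.960 = 0.947 is 0.828. That reproduces the stated 83%. The exact t-test with 18 degrees of freedom gives 78.5%. This gap is a separate matter, but 78.5% is the t-test starting point for the power figures below.

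**Variance of the two estimates.** Assumptions: normal data, 10 per arm, the same rho in both arms, Day 0 SD 1, control Day 14 SD 1, mouthwash Day 14 SD m. The pooled slope is b = rho(1+m)/2.

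- Change score: variance proportional to (2 - 2rho) + (1 + m² - 2rho·m).
- Adjusted: variance proportional to [(1 + b² - 2b·rho) + (m² + b² - 2b·rho·m)] × 17/16, where 17/16 = 1 + 1/(20 - 4) is the cost of estimating the slope.

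Example, m = 1 and rho = 0.5: change 1 + 1 = 2; adjusted (0.75 + 0.75) × 17/16 = 1.594; ratio 0.797.

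Ratio of adjusted to change-score variance:

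| m | rho 0.3 | 0.5 | 0.7 | 0.8 | 0.9 | 0.95 |
|---|---|---|---|---|---|---|
| 0.5 | 0.519 | 0.588 | 0.646 | 0.662 | 0.654 | 0.623 |
| 1 | 0.691 | 0.797 | 0.903 | 0.956 | 1.009 | 1.036 |
| 1.25 | 0.772 | 0.887 | 0.995 | 1.040 | 1.062 | 1.028 |
| 1.5 | 0.841 | 0.954 | 1.044 | 1.062 | 1.018 | 0.913 |

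For m = 1 the ratio is (1+rho)/2 × 17/16, which equals 1 at rho = 32/17 - 1 = 0.882. Break-even is 0.71 at m = 1.25 and 0.59 at m = 1.5. At m = 0.75 or 0.5 there is none. The worst ratio is 17/16 = 1.0625, reached when the best slope happens to be 1; the largest simulated ratio was 1.066. Simulation (100,000 trials per setting) otherwise agrees, for example 0.801 at rho 0.5 and 1.001 at rho 0.88 for m = 1.

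**Chance imbalance.** Under simple randomization the Day 0 mean difference has SD sqrt(2/10) = 0.447, so a difference above 0.5 SD in either direction has probability 0.264. Under stratified blocks (assumed: reflux and PPI use each 50% and independent, block size 2 or 4) it is 26-27%, about 24%, 19-20% or 13-15% if the strata explain 0, 10, 30 or 50% of the variance. With equal SDs, a 0.5 SD imbalance shifts the expected change-score estimate by 0.5 × (1 - rho) = 0.35, 0.25 or 0.15 SD at rho 0.3, 0.5 or 0.7. Adjustment removes this shift.

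**Power, change score to adjusted (simulated).**

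| Meaning of 1.3 SD | rho 0.3 | 0.5 | 0.7 | 0.8 |
|---|---|---|---|---|
| SD of change, m = 1 | 79% to 91% | 79% to 87% | 79% to 82% | 78% to 80% |
| Single-day SD, m = 1 | 64% to 80% | 78% to 87% | 94% to 96% | 99% to 99% |
| Single-day SD, m = 1.5 | 52% to 59% | 65% to 67% | 83% to 82% | 94% to 92% |

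Type I error of the adjusted test was 4.8-5.1% with equal SDs and 5.0-5.7% with m from 0.5 to 1.5; the planned t-test gave 4.9-5.5%.

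**Scale.** These figures compare the two methods on one approximately normal scale. The plan names untransformed abundance, so the standard adjusted interval was also checked on lognormal data (assumed) with a 75% reduction. Coverage of the nominal 95% interval for the difference in means:

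| Log SD | Method | log-scale rho 0.3 | 0.5 | 0.7 | 0.9 |
|---|---|---|---|---|---|
| 1.0 | Adjusted | 85% | 84% | 82% | 78% |
| 1.0 | Change | 95% | 94% | 93% | 90% |
| 1.5 | Adjusted | 75% | 73% | 70% | 63% |
| 1.5 | Change | 92% | 91% | 89% | 84% |

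The untransformed adjusted estimate also shrinks toward zero, by about 2-12% at log SD 1.0 and 4-25% at 1.5, although its power is higher and its mean squared error lower. On the log scale, adjusted coverage was about 95% and the variance gains in the m = 1 row held. That row is the relevant one for a constant proportional reduction, which leaves the log-scale SD unchanged. Rows with m above 1 describe subjects who respond to differing degrees.

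**The case against.** The planned analysis is legitimate. It is a randomized comparison, it already uses Day 0 data, it answers Hypothesis 1 directly, and a t-test on change is a common choice in a 20-subject pilot. The gain rests on a correlation and SDs that the documents do not supply: at rho 0.8 it is 4%, at 0.9 it reverses, and a 25% rise in mouthwash-arm spread is enough to remove it above about 0.7. Adjusting on the untransformed scale would also give a pilot meant to inform later studies a worse confidence interval than the planned one.

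All of this stands, and it limits the point in three ways.

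- A reader might infer that the change-score test is biased or inflates type I error. The documents do not support that: allocation is randomized, so the estimate is unbiased over randomization, and the simulated error rate is near 5%.
- A reader might infer that adjustment must be better here. Nothing in the documents fixes rho or the SDs, so that cannot be claimed.
- A reader might infer that adding Day 0 as a covariate to the plan's untransformed outcome is enough. With skewed abundance the coverage table shows otherwise.

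What the objection does not remove is the asymmetry. Under approximate normality the loss from adjusting is capped at about 6-7% of variance, while the gain is 20-31% at rho 0.3 to 0.5 with equal SDs and 33-48% if the mouthwash-arm SD halves. The documents give no reason to expect rho high enough for subtraction to be the better choice.

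**Conclusion.** The point holds as a cheap improvement in efficiency and in protection against chance Day 0 imbalance. It is not an error in the plan. Its size is conditional on assumed values: with equal SDs, variance about 31% lower at rho 0.3, falling to 4% at 0.8 and to nothing near 0.88, with earlier break-even if mouthwash-arm spread rises. The worst case is a loss of about 2 power points in the scenarios run. The conclusion requires an approximately normal analysis scale, which is why it is tied to log-transformed abundance. The calculations do not cover a large share of undetectable values, which could upset normality on the log scale too. It merits a change to the plan, with medium confidence.

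**What to change.** Before outcome data are examined, make the saliva primary analysis a linear model of log-transformed Day 14 *F. nucleatum* on arm and log-transformed Day 0 *F. nucleatum*. Prespecify how values below the detection limit are handled. Report a two-sided 0.05 test and a 95% CI for the arm effect, expressed as a ratio. Use the same model for the oral swab, and keep the mean and SD of change per arm as a descriptive summary. Do not apply the standard adjusted interval to untransformed skewed abundance.

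The cost is wording in the Statistics section and no new data. The downsides are one degree of freedom, the possible 6-7% variance loss if rho is very high or Day 14 spread rises, and a primary effect stated as a ratio instead of a difference in mean absolute abundance. Adding the two stratification factors (two more degrees of freedom) is a separate decision. The gastric cardia comparison has no Day 0 sample and is unaffected.

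### Randomization is stratified by reflux and PPI use, but the gastric cardia t-test ignores both; if they are prognostic, the test is conservative and gives up power

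*Combined protocol and SAP*

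**What the plan says.** - *Treatment arm assignment*: "We will perform blocked randomization stratified by the presence of gastro-esophageal reflux" (taken from the Reflux Assessment Questionnaire), "as well as by regular PPI use".
- *Statistics*, on the second hypothesis: mean *F. nucleatum* abundance will be calculated "in the cardia of the treated and untreated groups, and compare means using t-tests". No covariate is named there or in any other analysis, and no transformation of the qPCR values is stated. Esophageal brushings are to be handled the same way as a secondary analysis.
- *Statistics*, on testing: "All analyses will be 2- sided", and "For the primary analyses, statistical significance will be defined as" p < 0.05.
- *Specimen collections*: "At the Day 0 visit we will collect saliva and also swab the inside of the mouth". Brushings and biopsies are taken only at the Day 14 endoscopy, so the cardia has no baseline measurement.
- *Sample Size Considerations*: 20 subjects (10 per arm) are said to give 83% power for a 1.3 SD difference. With allowance for losses, "We therefore plan to enroll 22 subjects".
- The opening background text, on the esophagus in reflux esophagitis or Barrett's: "Also observed is an increased abundance of" *F. nucleatum*. Nothing in the documents links reflux or PPI use to *F. nucleatum* in the cardia.

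**The concern.** Stratified blocking forces the arms to be similar on reflux and PPI use. If these factors predict cardia *F. nucleatum*, the difference in arm means varies less from one allocation to another than it would under simple randomization. The two-sample t-test does not know this. It still counts the spread between strata as noise within each arm, so its standard error is too wide.

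The consequence is lost efficiency. The estimate stays unbiased and false positives do not increase, but the test runs below its nominal 5% and detects a real effect less often than an analysis that respects the design. The cardia comparison addresses one of the trial's two stated hypotheses and has only 20 subjects.

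The point does not carry over to saliva, which is analysed as change within each person. If the factors explain nothing in the cardia, the planned t-test is simply valid.

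**Working it through.** **1. The plan's own figure.** Inputs from *Sample Size Considerations*: n = 10 per arm, difference 1.3 SD, α = 0.05; two-sided from *Statistics*. The noncentrality is 1.3 × √(10/2) = 2.907.

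- Normal approximation: Φ(2.907 − 1.960) = Φ(0.947) = 82.8%, which is the stated 83%.
- Exact two-sided t-test, 18 df, critical value 2.101: 78.5%. This is the fair baseline for what follows.

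**2. Size of the mismatch.** Let R² be the share of outcome variance explained by the two factors. With arms perfectly balanced within strata, the true variance of the arm difference is (4/N)σ²(1 − R²), while the t-test estimates about (4/N)σ². Its standard error is therefore too large by a factor of 1/√(1 − R²): 1.054 at R² = 0.1, 1.118 at 0.2 and 1.195 at 0.3. Balance is imperfect with 20 subjects in four strata. In simulation at R² = 0.2 the excess was 7–11%, against the limit of 12%.

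**3. Adjusted analysis under perfect balance.** Noncentrality 2.907/√(1 − R²), 16 df, critical value 2.120:

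- R² = 0: 2.907, power 77.9%
- R² = 0.1: 3.064, power 82.0%
- R² = 0.2: 3.250, power 86.2%
- R² = 0.3: 3.474, power 90.3%

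**4. Simulation, normal errors.** 30,000 trials per scenario; 20 analysed out of 20 or 22 randomized; blocks of 2 or 4; strata (neither / PPI only / reflux only / both) either 25% each or 10/5/15/70%; equal additive effects of the two factors; effect 0 or 1.3 total SD. R², block size and strata shares are assumptions, because the documents give none of them. The two-sample t-test is compared with a linear model containing arm, reflux and PPI use.

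| R² | t-test type I error | t-test power | adjusted power | change (points) |
|---|---|---|---|---|
| 0 | about 5% | 77.5–78.3% | 74.9–77.2% | −2.8 to −1.0 |
| 0.1 | 4.0–4.3% | 78–79% | 80–81% | +0.9 to +2.3 |
| 0.2 | 3.1–3.8% | 79–80% | 84–86% | +4.7 to +5.6 |
| 0.3 | 2.3–3.1% | 80–81% | 89–90% | +8.4 to +9.4 |

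Adjusted type I error was 4.8–5.3% throughout. Break-even lies at R² of about 0.02–0.08. Repeat simulations agreed within simulation error.

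**5. Is stratification the cause?** At R² = 0.3 with unstratified 1:1 allocation the t-test's type I error is 4.8%. With stratified blocks of 4 it is 2.4%. The shortfall comes from stratifying and then ignoring the strata.

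**6. Skewed raw data.** As an illustration, the outcome is log-normal with log SD 1.5 and is analysed untransformed; R² and the effect are on the log scale. Type I error is 1.3–2.6% for the t-test and 2.3–2.7% adjusted, so neither reaches 5%. Power is about 33–44% for both. Change in power from adjusting, in points:

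| R² | equal strata | uneven strata |
|---|---|---|
| 0.1 | +0.7 to +1.0 | −1.8 to −1.4 |
| 0.2 | +3.2 to +3.5 | −0.6 to +0.1 |
| 0.3 | +6.2 to +6.4 | +0.5 to +1.1 |

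At R² = 0 the change is −2.2 to −1.2 over both strata patterns.

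**7. Sparse strata.** In the uneven pattern one factor was constant in about 4% of trials, the two factors coincided in about 1%, and a factor level held only 1–2 subjects in 38–40%. With normal errors, adjusted type I error stayed at 4.8–5.3% with these trials included.

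**The case against.** The strongest reply is that nothing in the documents shows the condition is met. The background observation concerns the esophagus in reflux esophagitis or Barrett's, not questionnaire-defined reflux, and says nothing about PPI use. *Sample Size Considerations* says no published data were available for a power calculation. At R² = 0 adjustment costs power, and the documents do not show on which side of break-even this trial lies. That stands, and it is why the concern is conditional.

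Second, the larger gains need roughly normal errors, while the plan compares means of qPCR abundance on an unstated scale. In the skewed illustration both tests have low power, and the choice of scale matters more than the covariates. That also stands, so the scale has to be fixed together with the model.

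Third, power of the planned test at 1.3 SD does not fall as R² rises (77.5–78.3% at R² = 0, 80–81% at 0.3). Even at 0.8 SD it falls by only about 0–2 points, from 39% to 37–39%. This is correct: the loss is relative to the adjusted analysis, not to the stated power.

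Fourth, a conservative t-test in a small pilot is valid. It is, but the factors were judged important enough to stratify on, and using them needs no new data. Two main effects did not disturb the type I error under normal errors, even with sparse strata.

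**Conclusion.** The concern holds as a conditional loss of efficiency. If reflux and PPI use are prognostic for cardia *F. nucleatum* and errors are near normal on the analysis scale, the planned test runs below 5%. It then gives up about 1–2 points of power at R² = 0.1, about 5 at 0.2 and about 9 at 0.3. If the factors explain nothing, the t-test is valid and adjusting would cost about 1–3 points. With strongly skewed raw values the benefit can disappear, and neither analysis attains 5%.

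There is no bias and no inflation of false positives. The size rests on an assumed R², since the documents give none, so confidence is moderate. The change is worth making because it is inexpensive and matches the analysis to the randomization, but the plan is not invalid without it.

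**What to change.** For the gastric cardia comparison, replace the t-test as the main analysis with wording such as:

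> Arms will be compared with a linear model containing treatment arm, reflux (yes/no) and regular PPI use (yes/no), as used in the randomization, as main effects. The arm coefficient will be reported with its 95% CI and two-sided p-value. A factor with only one level in the analysis set will be omitted. If reflux and PPI use coincide completely, only reflux will be kept. The unadjusted t-test will be reported as a sensitivity analysis.

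State the analysis scale (raw or a named transformation) in advance, because the benefit depends on it. Because the esophageal brushings are to be analysed like the cardia, they would follow the new model; one sentence should say so. Keep the planned t-test as primary for change in saliva, with adjustment at most as a sensitivity analysis, and keep the Wilcoxon test for %GNB.

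The cost is SAP wording only, since both factors are already recorded for randomization. The model uses two degrees of freedom and loses about 1–3 points of power if the factors are not prognostic. With skewed raw data and uneven strata it can lose up to about 2 points even at R² = 0.1.
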